The study will produce scientifically strong evidence as to whether two alternative models of community HIV screening among FSW (assisted and unassisted) result in (1) increased rates of formal HIV testing at health facilities and (2) increased rates of treatment initiation in districts in which the community screening intervention is added to the existing FSW community outreach model.

Two alternative study protocols are described in this document. The bulk of this document presents a protocol for a community randomized controlled trial (cRCT), which is the preferred research design option. However, due to a delay in procurement of the OraQuick® rapid HIV test kits that are to be used in the study, there may be insufficient time to undertake a full cRCT.¹ Accordingly, a contingency protocol that can be implemented in a shorter period of time is also presented.

6. Study Objectives

The primary objectives of this study will provide answers to the following five (5) questions:

1. Does the proportion of FSW who know their HIV status increased?

¹ All research activities must be completed by 31 December 2020.

2. Does the introduction of community HIV screening among FSW increase the rate of HIV testing at health facilities?
3. Does “assisted” or “unassisted” community HIV screening among FSW result in a larger increase in the rate of HIV testing at health facilities?
4. Does “assisted” and “unassisted” community HIV screening among FSW results in a larger increase in the rate of HIV positive case finding?
5. Does the introduction of community HIV screening among FSW increase the rate of initiation of ART?

The secondary objectives of this study will provide answers to the following two (2) questions:

1. What is the acceptability of community-based self-screening for FSWs participating in this study?
2. What is the satisfaction of FSWs participating in this study towards delivery of community-based self-screening?

B. STUDY DESIGN

1. Design Summary

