The flowchart of the study is presented in Figure 1. Randomization was carried out among the 23 priority districts in this study with a ratio of 2:1 (that is, 2 intervention districts per 1 control district). The details of randomization are explained in section B.4 of this document. **The assigned 15 intervention districts and 8 comparison districts** are described in Table 6. Potential participants in the intervention area will be screened through the inclusion and exclusion criteria established for

this study. The criteria for participants who are eligible for this study are explained in section B.3 of this document and Annex2.

According to the Indonesian Ministry of Health's current recommendation, HIV blood test at an authorized health facility is still the current practice for HIV diagnosis. Both participants in the intervention and comparison area will be offered for HIV blood test at a health facility. Participants in comparison areas and participants in intervention areas who agree to take HIV test at a health facility will then be managed further according to the existing guideline or "standard of care." For participants in intervention areas who refuses to have her blood drawn for HIV test at a health facility will then be offered self-testing using OraQuick®. Participants will then fill and sign the informed consent to participate in CBS study.

Next, participants will be offered to do the test assisted or unassisted. If the participant chooses to perform the test assisted, the PL/PE will help her from filling in a baseline survey, performing the test, and filling in a post-test survey. If the participant chooses to perform the test unassisted, there will be two options for the participant to get the test kit. First, PL/PE will deliver the test kit for the participant, help with filling in the baseline survey on the spot and give information about uploading test results and the post-test survey, along with a hotline number to call for any questions and concerns, including follow-up steps after participants have received the results. The second method, participants will be given a link online which will entitle information of this study, eligibility criteria, informed consent, baseline survey, link to order a test kit, link to upload result and link to fill in the post-test survey. Participant who chooses this second method will also be given hotline number should there be any further inquiries.

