Sample size requirements for the third question measurement pertains to the number of FSW who test positive for HIV at a health facility and are thus eligible to initiate treatment. This will depend upon (1) the number of FSW presenting at health facilities for testing and (2) the positivity rate among those tested. Sample sizes should thus be calculated accordingly. If we assume a testing positivity rate of 3%, it is apparent that the expected number of FSWs who would be eligible for treatment will be small and we will lack sufficient statistical power to make meaningful comparisons with comparison districts. For this reason, it is recommended that the impact of community screening among FSW be measured using SIHA data for FSW in both intervention and comparison districts. This estimate of impact derived in this way will be confounded if it were to be the case that interventions other than HIV self-testing were to be better implemented in intervention vs. comparison districts. It might be possible to minimize this potential bias by including measures of intervention implementation performance in the intervention and comparison districts in multivariable analyses. Thus, a large enough sample size is required to ensure sufficient power to determine the difference in the intervention and control districts.

C. THE INTERVENTION

1. General Description of The Intervention

FSW who meet the eligibility criteria will be offered for HIV blood test first. Participants who wish to take the test will then managed according to the current guideline for standard of care. Participants who disagree to take HIV blood test will then be offered screening test with Ora-Quick®. There will be with two options for community HIV screening by Peer Leaders: (1) in a convenient community setting assisted by PL/PE (assisted screening) or (2) in a setting of their own choosing without assistance from PL/PE (unassisted screening). FSW will also be able to access a community-based screening test by following online link from messages spread through WhatsApp number without having to come into contact with outreach workers. The saliva-based Ora-Quick® test kit will be used for community screening.

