In the event that participants' data are collected by paper, a procedure to upload the data into the established online system will be developed. Each data manager in the IUs needs to conduct the procedure regularly. This is to ensure that all data are being captured thoroughly.

F. DATA ANALYSES

The data analyses to be undertaken will be directed to addressing the research questions laid out at the beginning of the protocol and statistical tests appropriate to each specific analysis will be performed to inform the interpretation of results. The specific steps in the data analysis will be as follows:

1. Compare the characteristics of FSWs who receive self-testing and blood testing.

2. Compare the characteristics of FSWs who receive assisted and unassisted self-testing.
3. Compare proportion of FSWs taking confirmatory test out of those who receive the test in the assisted and unassisted self-testing.
4. Compare the proportion of FSWs who receive HIV test out of those who got offered for the test (including self-testing) in the intervention group with proportion of FSWs who receive HIV test in the control group.
5. Compare the proportion of FSWs taking confirmatory test (including self-testing) out of those receive the test in intervention groups and control group.
6. Compare the proportion of HIV positive in the assisted, unassisted (intervention) and HIV positive in the control group.
7. Compare the proportion of ART initiation in the assisted, unassisted (intervention) and the control group.
8. Calculate the cascade of HIV testing and treatment.
9. Compare stigma scores and FSWs who went to a health facility for HIV testing between assisted, unassisted group.
10. Compare the HIV and STI risk behaviors between assisted and unassisted group.

G. CONTINGENCY STUDY DESIGN

Should the OraQuick® test kits not become available in sufficient time to conduct a full-scale cRCT, a smaller-scale study will instead be undertaken. The purpose of the smaller study is the same as the cRCT described above, and the same protocol described above will be implemented. But the comparison is achieved targets between before and after intervention – there will be no comparison districts. The study will be undertaken in three (3) districts. The three districts will be selected from different parts of Indonesia, and they are: Kota Bandung (west part of Indonesia), Kota Denpasar (central part of Indonesia), and Kota Makassar (center-east part of Indonesia).

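### Section F items 6 and 7 compare self-screened women, essentially decliners of facility testing, with the whole control group and omit intervention women who accepted a blood test, so Section F lists no randomised-district comparison of case finding or ART initiation

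*Combined protocol and SAP*

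**What the plan says.** Item 6 of Section F reads "Compare the proportion of HIV positive in the assisted, unassisted (intervention) and HIV positive in the control group". Item 7 reads "Compare the proportion of ART initiation in the assisted, unassisted (intervention) and the control group". Neither states a denominator. Items 6 and 7 of the contingency design in Section G keep the same screening groups and add the three-district setting.

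Sections B.1 and C.1 say how women reach the assisted and unassisted groups. Every eligible woman in an intervention district is first offered a blood test at a health facility. An intervention participant "who refuses to have her blood drawn for HIV test at a health facility will then be offered self-testing using OraQuick"; section C.1 repeats this: "Participants who disagree to take HIV blood test will then be offered screening test with Ora-Quick". Row 6 of the E.3 recording table and item 7 of the Annex 2 eligibility form follow the same order. C.1 also describes an online route to a kit "without having to come into contact with outreach workers".

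Objective 4 in section A.6 asks whether assisted and unassisted screening "results in a larger increase in the rate of HIV positive case finding". Objective 5 asks whether introducing community screening raises the rate of ART initiation. Section A.5 describes the aim for treatment as higher initiation in the districts where screening is added.

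Item 4 of Section F already uses a wider population: "Compare the proportion of FSWs who receive HIV test out of those who got offered for the test (including self-testing) in the intervention group", set against the control group.

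**The concern.** Districts were randomised. A woman's refusal of a facility test comes later, and it decides whether she enters the assisted or unassisted group. Items 6 and 7 label those two groups as the intervention and compare them with a control group that is not divided by refusal. This has two consequences.

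- Positives and ART starts among intervention women who accepted the blood test are not counted on the intervention side, while their counterparts are counted in control.
- The contrast mixes the effect of the intervention with the difference between decliners and other women. Question 16 of the baseline questionnaires (Annexes 4 and 6) lists both low perceived risk and fear of a positive result as reasons for declining. The first would make the intervention look worse and the second would make it look better, so the direction of bias cannot be known in advance.

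Self-screening finds extra cases mainly by testing more women. It need not change the share of tests that are positive. A positivity proportion can therefore stay flat, or fall, while the number of cases found rises. Objectives 4 and 5 are listed as primary, so a real gain could be reported as none.

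**Working it through.** The plan gives no sample size or expected result for items 6 and 7, so there is no stated figure to reproduce. The check is a count per 1,000 eligible women offered testing in each arm.

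**Inputs from the documents (section B.5)**
- Facility testing p = 0.50. This is the comparison-group proportion, which the plan chose as a worst case for sample size and does not present as an expected rate.
- Positivity = 3%.

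**Assumptions (the documents give no values)**
- Facility testing is the same in both arms.
- Uptake u = 60% of decliners are screened.
- Positivity among decliners is also 3%.
- Every reactive screen is confirmed.

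**Counts**
- Control: 1,000 × 0.50 = 500 tested; 500 × 0.03 = 15 positive.
- Intervention, accepters: 500 tested, 15 positive.
- Intervention, decliners: 500 × 0.60 = 300 screened; 300 × 0.03 = 9 positive.
- Cases found: 15 + 9 = 24 versus 15; 24/15 = 1.60, or +60%.

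**What item 6 would show under each plausible denominator**
- Among those tested: 9/300 = 3.0% versus 15/500 = 3.0%; ratio 1.0.
- Among those offered self-screening (control: offered a test): 9/500 = 1.8% versus 15/1,000 = 1.5%; ratio 1.2.
- Among all offered testing: 9/1,000 = 0.9% versus 15/1,000 = 1.5%; ratio 0.6.

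None recovers 1.60, because the 15 positives among intervention accepters are missing from the numerator.

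**Item 7.** Suppose the same share s of confirmed positives starts ART in every group. Read as a proportion of positives, item 7 shows s versus s. ART starts per 1,000 offered are 24s versus 15s.

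**Sensitivity to p and u.** With equal positivity and full confirmation, the gain is u × (1 − p)/p.

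| Facility testing p | u = 30% | u = 60% | u = 90% |
|---|---|---|---|
| 30% | +70% | +140% | +210% |
| 50% | +30% | +60% | +90% |
| 70% | +13% | +26% | +39% |

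**Sensitivity to confirmation.** If half of reactive screens are confirmed, each gain halves. The central case becomes 15 + 4.5 = 19.5 versus 15 (+30%). Item 6, read as confirmed positives among those tested, then shows 4.5/300 = 1.5% versus 3.0%, an apparent loss while more cases are found.

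**Sensitivity to decliner positivity.** At 2% among decliners the gain is multiplied by 2/3. Combined with half confirmation, the smallest cell becomes 0.129 × 2/3 × 1/2 = 0.043, about +4%. If decliners had higher positivity than other women, item 6 read among those tested and with full confirmation would lean in favour of screening, for reasons of selection.

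**The case against.** A reader might infer that the plan cannot answer Objectives 4 and 5 at all. The documents do not support that.

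- For treatment, section B.5 recommends measuring impact with SIHA data for FSW in both intervention and comparison districts. That would include accepters. However, it is only a recommendation, B.5 itself warns of confounding by other interventions, section E.3 says the study relies mainly on outreach records, and no Section F item includes it.
- Objective 4 is partly worded by screening method, so a by-method result has some relevance. Positivity among screened women is still not a case-finding rate.
- Item 8 adds a testing and treatment cascade, but with no defined population or comparison.

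A reader might also infer that every self-screened woman has refused a facility test. The online route makes this too absolute: the link contents listed in B.1 include no facility-test offer, although Annex 2 and the unassisted recording list in E.3 point the other way. Nor does control lack the split: E.3 row 3 records agreement and refusal there too, but items 6 and 7 do not use it. Control tests may also take place at mobile clinics (section C.4), so tested control women are not an exact counterpart of intervention accepters.

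The denominator of item 6 is not stated, so the 3% versus 3% result depends on one reading. That stands, but the other readings also fail to recover the contrast.

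Finally, B.5 concedes that few positives are expected and that power for the treatment comparison will be lacking. This limits what any analysis can show. It does not justify the wrong population.

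**Conclusion.** The concern holds in this form. Items 6 and 7, and their Section G counterparts, use groups formed after randomisation, omit intervention women who accepted blood testing, and state no denominator. As listed, Section F contains no randomised-district comparison of case finding or ART initiation. Section G has no randomised comparison to lose, but the omission of accepters carries over.

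In the central illustration, a rise from 15 to 24 cases per 1,000 offered appears as no difference in positivity. Across 30–70% facility testing and 30–90% uptake, the gain is about +13% to +210%, and it halves if half of reactive screens are confirmed. These figures show how far the measures can diverge and do not forecast the trial's effect. They rest on equal facility testing in both arms and equal positivity, and on uptake and confirmation values that the documents do not give. The omission of accepters follows from the text and needs none of these assumptions.

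**What to change.** 1. For the arm comparison, define the numerator of item 6 as all facility-confirmed positives and that of item 7 as all ART starts, by any route including accepted blood tests, in the allocated districts. Use all eligible women offered testing as the denominator for both. Apply the same definition in control, including mobile-clinic tests, and allow for district clustering.
2. Add a row to the E.3 table for facility-confirmed positives in both arms. The present rows count reactive screens and subsequent tests, but not the results of those tests. Annex 5 holds blood-test results, but the documents do not say that it is used in control districts.
3. Write the SIHA district comparison recommended in B.5 into Section F as a supporting analysis, with the confounding caveat that B.5 already gives.
4. Keep the assisted and unassisted proportions as descriptive cascade results under item 8.
5. Make the matching change to items 6 and 7 of Section G.

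The cost is modest. Offers and ART starts are already recorded in both arms (E.3 rows 2 and 10), and item 6 as written already needs control positives. The main additions are one recording row and the matching result data in control. The effect per woman offered will look smaller than a proportion among those tested. Women reached only through online broadcasts have no control counterpart, so the offered denominator does not fully restore the randomised contrast. The plan should state this as a limitation.

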A Community Randomized Controlled Trial (cRCT) will be used for this study to explore in the HIVST evidence for FSWs in Indonesia with tests and treatment results in intervention acceleration districts compared to control districts with the current standard of care. In the trial, it is recommended the candidates will be tested using two approaches (assisted and unassisted), the latter via direct, fixed and other means of distribution system. A direct distribution system is where and FSW participant is directly given and HIVST by a peer, and a fixed distribution system is where the FSW participant collects the HIVST from a fixed point such as health clinic. Other distribution system may be implemented using courier services such as GO-JEK, etc. This trial aims to determine the acceptability, effectiveness and safety of these HIVST delivery approaches compared with standard of care for improving HIV testing coverage and knowledge of HIV status.

The study will be undertaken in the 23 “acceleration” districts in the National AIDs Program. These are: Kota Medan, Deli Serdang, Kota Palembang, Kota Bandar Lampung, Kota Tangerang Selatan, Tangerang, Kota Jakarta Selatan, Kota Jakarta Timur, Kota Jakarta Pusat, Kota Jakarta Barat, Kota Jakarta Utara, Bogor, Kota Bekasi, Kota Bandung, Kota Depok, Kota Semarang, Kota Surakarta, Kota Malang, Kota Surabaya, Kota Denpasar, Kota Makassar, Kota Sorong and Kota Jayapura. These are districts with high HIV prevalence among HIV key populations, including FSW, and have comprehensive ongoing HIV-TB intervention packages consisting of both health services and community prevention and support programs. As for the FSWs program, these 23 priority districts already implementing a comprehensive outreach package (reach to test and simplified case management for FSWs living with HIV). Table 3 below shows Global Fund targets for FSW HIV testing in 23 priority districts for 2019-2020. Table 4 shows achieved target of HIV testing per semester in 2018-2019 and estimated numbers of direct and indirect FSW in 2012 (MoH, 2013). Table 5 shows achieved target of outreach per year in 2018-2019 in 23 priority districts.

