3.1 Study kick-off										
3.2 Data collection										
4. Data analysis and report writing										
5. Workshop for study finding dissemination										

3. Eligibility Criteria

The target audience for the intervention to be evaluated are FSW in Intervention districts that meet the criteria outlined below.

Inclusion criteria

- Women, 18 years or older at enrolment
- Reports transactional sex (vaginal, oral and/or anal) at least once in the past month
- No HIV test in last 6 months
- Self-reported HIV negative OR HIV status unknown

Exclusion criteria

- Unwilling to participate for any reason
- Concurrently participating in another HIV prevention study

4. Randomization

Stratified randomization was carried out for the 23 priority districts involved in this study. First, sampling strata were created by sorting the mean average value of achieved HIV testing target per semester from 2018-2019 in each district from the largest to the smallest. The second step was to sort the districts into eight groups of three districts, except for the last group which will only consist of two districts. Randomization for intervention and comparison group were then carried out within these groups of eight with 2:1 ratio (2 intervention: 1 comparison).² The results of stratified randomization are presented in Table 6. In separate table, Table 7 contains 15 intervention districts and Table 8 contains 8 comparison districts.

² A 2-to-1 intervention to comparison district ratio was chosen in order to increase the likelihood of recruiting a sufficient number of FSW for community screening to reach the sample size target considering the relatively short time frame available for for study implementation.

Table 6. Allocated intervention group and comparison group

No	Kab/Kota	Region	Achieved target of HIV testing per semester (2018-2019)	Group
1	Kota Denpasar	3	982	Intervention
2	Kota Makassar	3	866	Comparison
3	Kota Palembang	1	694	Intervention
4	Kota Jakarta Utara	1	612	Comparison
5	Kota Medan	1	575	Intervention
6	Kota Surabaya	3	568	Intervention
7	Kota Jakarta Barat	1	544	Intervention
8	Kota Bandung	2	487	Comparison
9	Kota Jakarta Timur	1	479	Intervention
10	Kota Jakarta Pusat	1	473	Intervention
11	Kota Jakarta Selatan	1	448	Comparison
12	Kota Sorong	4	415	Intervention
13	Kab. Tangerang	1	391	Intervention
14	Kota Bogor	2	374	Intervention
15	Kota Jayapura	4	323	Comparison
16	Kota Bandar Lampung	1	319	Comparison
17	Kota Depok	2	287	Intervention

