Except for outreach, all above mentioned activities are incentivized. Below are details of incentives given to PL/PE based on current standard program:

1. Cash incentive of 70,000 IDR for every client who referred for HIV testing to health facilities.
2. Cash incentive of 25,000 IDR for every client taking the test after being reached through mobile outreach.
3. Cash incentive of 50,000 IDR for every client with positive confirmatory test starting on ART.

5. Incentives for Participation

Incentives will be given for different participation role in this study:

1. For all eligible FSWs participating in baseline survey will be given 50,000 IDR
2. For FSWs taking VCT and reporting the results will be given 100,000 IDR
3. For FSWs doing CBS AND uploading/sending test result will be given 100,000 IDR
4. For FSWs participating in post-test survey (both assisted and unassisted) will be given 50,000 IDR
5. Cash incentive 100,000 IDR for transportation and registration and/or fee for confirmatory test for CBS **reactive result** for FSWs who go to health care facility for confirmatory test (assisted and unassisted)
6. Cash incentive 100,000 IDR for transportation and registration and/or fee for confirmatory test for CBS **non-reactive result** for FSWs who go to health care facility for confirmatory test (assisted and unassisted)

Incentives will be given for different role of PL/PE in this study:

1. For PL/PE who assists FSWs for taking self-screening (including filling in baseline and post-test) will be given 150,000 IDR
2. For PL/PE who delivers test kit to FSWs who opt for unassisted screening AND obtain baseline survey on the spot will be given 100,000 IDR

Incentives will be given for health facility:

For collecting data on FSWs who do confirmatory test (assisted and unassisted). Funds to cover additional operational cost will be given to each implementing unit (IU) for delivering test kit via Go-Pay/Grab Pay Top-Up to client's address.

D. LINKAGE TO HEALTH SERVICES FOR ARV INITIATION

Outreach workers will navigate clients to health care facilities for confirmatory test and ARV initiation if the result is confirmed as positive. Health care facilities in each district will be selected by their readiness to offer Test & Treat (T&T). Clients who come for confirmatory test are expected to be started for ARV initiation on the same day of confirmatory test.

E. DATA COLLECTION PROTOCOLS

1. Baseline survey

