- How likely is it that the client will get a HIV test at a health facility as a result of the community screening test, on a scale of 1-5
- Comments and suggestions.

3. Routine Recording

Because of limitations in the data recorded and reported by health facilities, the study will rely primarily upon data recorded by IU outreach staff. Modifications will be made to the data recording and reporting systems currently being used to facilitate collection of the data needed for the study in a manner that minimizes additional recording and reporting burden. The nature of the adjustments to be made will be different for "assisted" and "unassisted" community screening.

To capture the data needed for of this study, the following data need to be recorded:

No	Data Recorded	Intervention Group	Control Group
1	Number of FSW contacted via outreach that were at least 6 months since their last HIV test for whom testing at a health facility was recommended	Yes	Yes
2	Numbers of FSW offered for HIV test at health facility	Yes	Yes
3	Numbers agreeing and disagreeing to testing at a health facility	Yes	Yes
4	Of those agreeing to getting tested at a health facility, the numbers that actually went to a health facility and were tested for HIV	Yes	Yes
5	Number of FSW offered for OFT screening	Yes	No
6	Among FSW not agreeing to be tested at a health facility, the numbers that agreed to (1) assisted community HIV screening and (2) unassisted community HIV screening	Yes	No
7	Numbers that were actually screened, assisted and unassisted	Yes	No
8	The number of community screening tests that were reactive	Yes	No
9	Among FSW with reactive community screening tests, the numbers that were subsequently tested at a health facility	Yes	No
10	Number of FSW initiating ART	Yes	Yes

For **unassisted** approach, additional information will be gathered as indicated below:

1. Numbers of FSW who access the link online
2. Numbers of FSW who are deemed eligible
3. Numbers of FSW who fill in baseline survey and agree to participate
4. Numbers of FSW who agree to take HIV test at health facility
5. Numbers of FSW who request the kit being delivered vs picking-up at fixed location
6. Numbers of FSW who upload the test result
7. Numbers of reactive vs non-reactive test result
8. Numbers of FSW who complete the post-test survey

9. Among FSW with community screening tests, the numbers that were subsequently tested at a health facility (reactive OR non-reactive)
10. Number of FSW initiating ART

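### The case-finding comparison (section F, item 6) does not separate new from previously diagnosed infections, so known positives can be counted at different rates in the two arms

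*Combined protocol and SAP*

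**What the plan says.** - **Objective.** Objective 4 in A.6 asks whether assisted and unassisted screening "results in a larger increase in the rate of HIV positive case finding".
- **Analysis.** Section F, item 6 reads "Compare the proportion of HIV positive in the assisted, unassisted (intervention) and HIV positive in the control group". It does not limit positives to new diagnoses, say whether positive means screen-reactive or confirmed, or give a denominator. Item 7 compares ART initiation across the same groups, also without a denominator.
- **Entry.** B.3 requires "Self-reported HIV negative OR HIV status unknown", and introduces its criteria with "The target audience for the intervention to be evaluated are FSW in Intervention districts that meet the criteria outlined below". Annex 2 collects the answer as a checklist.
- **Recording in both arms.** Row 1 of the table in E.3 sets one condition only, time since the last test: it counts women reached by outreach who were six months or more from a test and were advised to test at a facility. No row carries HIV status at contact, and no row counts facility-positive results.
- **Forms.** Question 13 in Annexes 4 and 6 asks when the last HIV test was, not what it showed. Annex 5 (facility test) records reactive or non-reactive; Annex 7 (oral fluid test) adds indeterminate. The identifiers in E.4 prevent a woman from taking part twice; they do not reveal an earlier diagnosis.
- **Payments.** C.5 lists payments to women, starting with "For all eligible FSWs participating in baseline survey will be given 50,000 IDR". C.4 describes an unchanged control programme whose listed payments go to peer leaders and educators, including 70,000 IDR per client referred for facility testing.
- **Existing records.** B.1 says that all 23 districts already run "simplified case management for FSWs living with HIV".

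**The concern.** Re-testing a woman who already has a diagnosis finds nobody, yet under item 6 she counts the same as a new case. Facility confirmation does not remove her, because a known positive confirms as positive. If known positives come forward at different rates in the two arms, the comparison mixes case finding with re-counting.

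There are documented reasons why the rates could differ. The status criterion is written for one arm only, and payments to women are listed only for the study. Testing targets and payments to staff per client referred also operate in the control programme.

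Item 7 can be affected too. A woman already on ART cannot initiate it. If the denominator there is all positives, which the plan does not say, such women lower the initiation proportion. One omission could thus distort the comparisons for two primary objectives, 4 and 5.

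**Working it through.** **Inputs from the documents**
- Positivity among those tested: 3% (B.5), taken here as the true rate of undiagnosed infection in both arms.
- Group size: 761 (B.5).
- Payments: C.5.

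**Input that is assumed.** The share *f* of tested women who are already diagnosed. The documents give no figure, so several pairs are shown.

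**The plan's own figure.** With proportions 0.5 and 0.6, 90% power and one-sided 5%, the calculation gives 423 per group. Then 423 × 1.5 = 634.5, rounded up to 635, and 634.5 × 1.2 = 761.4, matching 761. (The printed Z of 1.96 would give 519 × 1.5, about 779; that is a separate matter and does not bear on this point.) The 761 was set for the facility-testing outcome. It serves here only as a convenient scale.

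**Payments per completed route**
- Facility test: 50,000 + 100,000 = 150,000 IDR.
- Self-test: 50,000 + 100,000 + 50,000 = 200,000 IDR.
- Self-test plus confirmatory visit: 200,000 + 100,000 = 300,000 IDR, of which the last 100,000 is for transport, registration and/or fee.

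The baseline survey alone pays 50,000 IDR.

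**Expected positives.** 761 × 0.03 = 22.8, about 23.

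**Effect of known positives.** Observed positivity = *f* + (1 − *f*) × 0.03:
- *f* = 1%: 0.01 + 0.99 × 0.03 = 3.97%
- *f* = 2%: 0.02 + 0.98 × 0.03 = 4.94%

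| Known positives, intervention v control (assumed) | Observed positivity | Ratio |
|---|---|---|
| 1% v 0% | 3.97% v 3.00% | 1.32 |
| 2% v 1% | 4.94% v 3.97% | 1.24 |
| 2% v 2% | 4.94% v 4.94% | 1.00 |
| 1% v 2% | 3.97% v 4.94% | 0.80 |

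The true ratio is 1.00 in every row. Counting only new diagnoses removes the known positives from the numerator. The remaining difference in the denominator is negligible: with 1% v 2% known, 2.97% v 2.94%.

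**Composition at *f* = 1%.** Known positives: 761 × 0.01 = 7.6. New: 761 × 0.99 × 0.03 = 22.6. Share not new: 7.6 / 30.2 = 25%.

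**Item 7 at *f* = 1%.** If all known positives were already on ART and the denominator were all positives, the highest attainable initiation proportion would be 22.6 / 30.2 = 75%, even if every newly diagnosed woman started treatment.

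**The case against.** A reader might infer that already-diagnosed women are counted in the intervention arm only, drawn in by payments of 150,000 to 300,000 IDR, so that the bias must favour the intervention. The documents do not support this.

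- B.1 offers the facility blood test in comparison districts too. C.4 gives their implementing units six-monthly testing targets and pays staff per client referred. The negative-or-unknown criterion is not written for those women, so control districts may filter out fewer known positives.
- The larger sums are totals for completing every step of a route, not payments for entry. C.5 names no arm; that control women are unpaid is inferred from the unchanged control programme.
- Item 6 is silent on the definition of positive. That it counts every positive is a reading of that silence.

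All of this stands, and it rules out a claim about direction. It does not rescue the measure: without a common definition of a case, the arms cannot be compared on case finding.

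B.5 recommends SIHA data for both arms where numbers are small. The documents do not say whether SIHA separates new from known cases, and E.3 says that the study will rely mainly on implementing-unit records.

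A further objection concerns linkage. Facility data are described as limited (E.3), and participants carry an identifier built from four letters of the name and the date of birth (E.4). This limits how complete a look-up can be, but does not prevent one at the testing facility.

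**Conclusion.** The point holds as a mismatch between primary objective 4 and its analysis. Item 6 measures positivity among those tested, without regard to earlier diagnosis. Status at entry is self-reported and required in writing only in intervention districts, and no form or record check would allow known positives to be identified afterwards.

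With about 23 positives expected per 761 women at 3%, one or two percentage points of known positives are enough to move the ratio materially. Over the assumed shares shown it runs from 0.80 to 1.32 with no true difference. Those shares are illustrations; the documents determine neither the size nor the sign of the bias. The effect on item 7 depends further on its unstated denominator and on how many known positives are already on treatment.

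This should be corrected: it aligns the measure with the stated objective at low cost.

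**What to change.** - Define an item 6 case, in both arms, as a facility-confirmed, newly diagnosed infection.
- For each confirmed positive in all 23 districts, have the testing facility record from its HIV/ART register whether the woman was previously diagnosed and whether she was already on ART. Use SIHA or implementing-unit case-management records as well where they can be linked. Apply the same procedure in both arms.
- Report previously diagnosed women separately.
- In item 7, exclude from the denominator only women already on ART. Women diagnosed earlier but untreated can still initiate and should stay in.

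Adding a shorter interval to question 13 would not help, since a woman who has denied a recent test on the eligibility form can repeat the denial. Checking the testing log for every entrant is not needed for this purpose.

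**Cost.** A small record look-up, limited to confirmed positives. Annex 5 already calls for validation at the facility, and C.5 already provides incentives to facilities for collecting confirmatory-test data. Reported positivity will be slightly lower, and some earlier diagnoses will be missed because facility data are limited and identifiers abbreviated.
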